4.1 Analysis Populations

Modified Intent-To-Treat (mITT): All randomized participants who have been exposed to study treatment (i.e., at least one dose of study drug).

Per-Protocol (PP): All eligible, randomized participants who 1) received all four study vaccination / placebo administrations, and 2) did not take any medication prohibited by the study protocol on or prior to their week 26 visit (as defined per protocol section 10.7.1).

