#### 6.2.3 Post-Entry Evaluations

Post-entry evaluations occur after the study entry visit and vaccination #1 administration at week 0. Study visits are scheduled as indicated in the SOE.

The visit window for the post-entry evaluations is  $\pm 14$  days.

Due to the feasibility challenges posed by the COVID-19 situation, starting 03/16/20, the visit window is broadened from  $\pm 14$  days to -14 days to +60 days. The broadened visit window is applicable to visits scheduled to occur before 04/30/20. This will be reviewed again at a later date to see if the 04/30/20 date should be extended (to include visits occurring after 04/30/20), and/or if the visit windows themselves need to be extended further. **See the update below.**

**Upon further review, the visit window is broadened from  $\pm 14$  days to -14 days to +180 days for visits that were planned to occur before 07/15/20. While +180 days is allowed, sites are encouraged to schedule the applicable visits within +90 days.**

The week 24 and week 26 visits should remain separate and coordinated to be as close to 2 weeks apart as feasible, but can be up to 60 days apart. Thus, if the week 26 visit has to be delayed, it is better to postpone the week 24 visit until the week 26 visit can occur 2 weeks later, or as close to that interval as possible.

NOTE A: The deferred study vaccinations #2, #3, and #4 should be performed within 14 days from the time of the previously scheduled week 4, week 12, and week 24 visits, respectively (see [section 6.3.10](#)).

NOTE B: After study entry, administration of non-HIV vaccines must occur more than 2 weeks prior to the scheduled study vaccination #2 (week 4), #3 (week 12), and #4 (week 24) injections.

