4.3 Visit Schedule and Analysis Windows

The schedule of evaluations is given in Section 6.1 the protocol. See timing of evaluations below:

- **Screening:** evaluations must be completed within 60 days prior to randomization (i.e., entry, week 0) unless otherwise specified.
- **Pre-Entry:** evaluations must be completed at least 24 hours after screening evaluations have been completed and at least 24 hours prior to entry evaluations unless otherwise specified.
- **Entry (week 0):** evaluations must occur at least 24 hours after pre-entry evaluations unless otherwise specified. Study entry or baseline is defined as the randomization date. The value used for baseline summaries will be the last evaluation on or before the randomization date. Participants must begin treatment within 72 hours after study enrollment.
- **Post-Entry:** evaluations occur after the study entry visit and vaccination #1 administration at week 0. The visit window for the post-entry evaluations is \pm 14 days.

- **Week 4** (vaccine #2 administration): weeks (2, 6]
- **Week 12** (vaccine #3 administration): weeks (10, 14]
- **Week 24** (vaccine #4 administration): weeks [22, 26]
- **Week 48**: evaluations will be completed at the participant's final on study visit and scheduled within a ± 14 days; weeks (46, 50].

Due to the delayed visits during the COVID-19 pandemic, starting 03/16/20, the visit window for week 24 and 48 was broadened from ±14 days to -14 days to +60 days. The broadened visit window was applicable to visits scheduled to occur before 04/30/20. Upon further review, the visit window was then broadened from ±14 days to -14 days to +180 days for visits that were planned to occur before 07/15/20. While +180 days was allowed, sites were still encouraged to schedule the applicable visits within +90 days. Thus, the new visit window for week 24 is weeks [22, 50] and week 48 is weeks [46, 74]

According to CM # 2, the week 24 and week 26 visits should remain separate and coordinated to be as close to 2 weeks apart as feasible, but can be up to 60 days apart. Thus, if the week 26 visit has to be delayed, it is better to postpone the week 24 visit until the week 26 visit can occur 2 weeks later, or as close to that interval as possible.

- Any deferred study vaccinations #2, #3, and #4 should be performed within 14 days from the time of the previously scheduled week 4, week 12, and week 24 visits, respectively.
- **Discontinuation Evaluations:**

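### The per-protocol set does not require vaccination #4 to precede the week 26 specimen, and the week-0-based analysis windows can pick the wrong specimen when visits were delayed

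*SAP*

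**What the plan says.** **Analysis set.** SAP 4.1 admits to the per-protocol set eligible randomized participants who "received all four study vaccination / placebo administrations" and who took no prohibited medication up to and including the week 26 visit. The time limit belongs to the second criterion only; the first has no date, order or interval. SAP 5.1 repeats both criteria and makes this set primary, with complete cases.

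**Visit windows.** SAP 4.3 lists the week 24 visit as "vaccine #4 administration): weeks [22, 26", closed at both ends. It has no line for week 26, the primary time point, so only the general ±14-day rule ("The visit window for the post-entry evaluations is" ±14 days) applies. Protocol 6.2.3 (Note A) and SAP 4.3 allow a deferred vaccination #4 up to 14 days from the previously scheduled week 24 visit. For COVID-19 delays the SAP states: "Thus, the new visit window for week 24 is weeks [22, 50] and week 48 is weeks [46, 74". Again, week 26 is not given.

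**Spacing.** Protocol 6.2.3 says: "The week 24 and week 26 visits should remain separate and coordinated to be as close to 2 weeks apart as feasible", with up to 60 days allowed. If week 26 must slip, "it is better to postpone the week 24 visit until the week 26 visit can occur 2 weeks later". The SAP carries the same text and attributes it to the COVID-19 memo: "According to CM # 2, the week 24 and week 26 visits should remain separate".

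**Analysis windows.** SAP 4.3 ends by cutting analysis windows at the midpoints between adjacent scheduled weeks. Where a window holds several evaluations, the one nearest the scheduled week is used.

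**The concern.** The primary endpoint is meant to show the response after the full four-dose regimen. A specimen drawn before vaccination #4 shows a three-dose response. The criterion as worded treats two equivalent participants differently. One who had three doses at the specimen and never received the fourth is excluded; one who had three doses at the specimen and received the fourth a few days later is included.

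A specimen taken before the fourth dose has had, or one taken very soon after it may have had, no time to reflect that dose. If the fourth dose adds to the response, such specimens dilute the two vaccine arms and leave placebo unchanged. The p24CE comparison with placebo then moves toward no difference in a set labelled per protocol.

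**Working it through.** **1. Ordinary windows (days from week 0).**
- Vaccination #4, SAP 4.3: weeks 22 to 26 = days 154 to 182.
- Week 26 visit, derived from ±14 days: weeks 24 to 28 = days 168 to 196.
- The permitted visits overlap in weeks 24 to 26.
- Midpoint cut between weeks 24 and 26: (24 + 26)/2 = week 25 = day 175. A specimen before day 175 is not a week 26 value.
- Earliest countable specimen minus latest dose: 175 − 182 = −7 days.
- Latest specimen minus earliest dose: 196 − 154 = +42 days.

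The intended interval is 14 days. The countable range is −7 to +42 days, and no per-protocol criterion limits it.

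**2. COVID-19 windows.**
- The plan's own limits reproduce after rounding: 24 + 180/7 = 49.7 (stated 50) and 48 + 180/7 = 73.7 (stated 74). The unstated week 26 limit would be 26 + 180/7 = 51.7.
- Upper midpoint for week 26, if no scheduled visit lies between: (26 + 48)/2 = week 37.
- Example: week 24 visit at week 30 and week 26 visit at week 32, exactly the 2-week spacing asked for. Both lie between weeks 25 and 37. Distances from week 26 are |30 − 26| = 4 and |32 − 26| = 6, so the rule takes the week 30 evaluation. If a specimen was drawn at that dosing visit, it becomes the week 26 value.
- A week 26 visit more than (37 − 26) × 7 = 77 days late is assigned to week 48. That lies within both the 180 days allowed and the 90 days encouraged.

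**3. Other safeguards in the text.** The COVID-19 sensitivity analysis in SAP 5.1 excludes delays of vaccinations #2 and #3, not #4. The mITT analysis would keep mistimed specimens.

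**4. Illustration of size.** Inputs from SAP 2.1: 20 v 10 randomized, 10% loss, response 0.64 v 0.10, two-sided Fisher, 5%. Evaluable: 20 × 0.9 = 18 and 10 × 0.9 = 9.

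Power = Σ P(X = x) P(Y = y) over all tables with Fisher p ≤ 0.05, where Y ~ Bin(9, 0.10) and X = Bin(18 − m, 0.64) + Bin(m, q). Here m is the number of mistimed p24CE participants and q their response rate. On the side favouring vaccine, rejection needs x ≥ 8, 10, 12 or 14 when y = 0, 1, 2 or 3, and so on.

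| m | q = 0.10 (placebo rate) | q = 0.37 (half effect, (0.64 + 0.10)/2) |
|---|---|---|
| 0 | 79.8% | 79.8% |
| 1 | 74.5% | 77.1% |
| 2 | 68.2% | 74.2% |

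The row m = 0 reproduces the plan's 80%. Both m and q are assumptions; the documents give neither.

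**5. Removing mistimed participants instead.** With the remainder at 0.64 v 0.10, power is 74.0% for 17 v 9 and 77.8% for 16 v 9. The non-monotone step comes from the discreteness of Fisher's test. Exclusion therefore does not reliably recover power, and the argument for the order condition is validity.

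**The case against.** The strongest reply is that the documents do state the sequence. Week 26 follows week 24 by about two weeks, and week 24 is to be postponed if week 26 slips. This stands as a description of intent: a specimen before the dose contradicts it, and a visit one day after the dose is hard to call as close to two weeks as feasible unless nothing better could be arranged. But the text sets a maximum and no minimum, and breaching it removes nobody from the per-protocol set. In the weeks 30 and 32 example the spacing is exactly as asked, and the selection rule still goes wrong.

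Three stronger readings are tempting and not supported:
- *A specimen 14 days before vaccination #4 could count.* The raw visit windows allow 168 − 182 = −14 days, but the midpoint rule stops at week 25, so the extreme is −7.
- *Visits before 03/16/20 had no spacing rule.* The SAP attributes the spacing text to the COVID-19 memo, but the schedule of evaluations (protocol 6.1), the deferred-vaccination section (6.3.10) and the section cited for the per-protocol definition (10.7.1) were not available. Any of them could hold such a rule.
- *Mistimed specimens occurred, or the plan prescribes them.* Nothing shows that even one did. The plan fails to exclude them.

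It is also fair that the power figures concern the binary Fisher comparison. The primary test is a Wilcoxon rank-sum test on Y, which the SAP expects to be more powerful.

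**Conclusion.** The point holds as a gap in the definition of the primary analysis set and a conflict between the analysis-window rule and the broadened visit windows. Under ordinary windows the exposure is narrow: specimens from 7 days before to a few days after vaccination #4. For COVID-delayed visits it is wider, because windows counted from week 0 can select a dosing-visit evaluation or move a true week 26 visit into week 48. The first outcome requires that a specimen was drawn at the dosing visit; the second, that no scheduled visit lies between weeks 26 and 48.

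In the illustration, one or two mistimed p24CE participants cost about 5 or 12 points of power if three doses give only the placebo rate, and about 3 or 6 points at half the effect. If three doses already gave the full response, nothing would be lost. The gap should be closed before unblinding. It does not show that the trial result is biased.

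**What to change.** 1. **SAP 4.1 and 5.1:** require that all four administrations were received before the week 26 immunogenicity specimen was collected.
2. **SAP 4.3:** identify the primary specimen as the one from the visit following vaccination #4, using the actual date of that vaccination, not midpoints counted from week 0. Reconcile this with the visit windows and spacing text in protocol 6.2.3 and SAP 4.3 and with the per-protocol definition. Any minimum interval is for the team to decide.
3. **Report** days from vaccination #4 to specimen, by arm.

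If protocol 6.1, 6.3.10 or 10.7.1 already holds an order rule, carry it into the SAP.

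The cost is a few sentences and one variable derived from the vaccination and specimen dates. The downside is that a mistimed participant leaves a small per-protocol set, although that participant stays in the mITT sensitivity analysis. No re-timing of visits is asked for. SAP version 2.0 took effect on 09/10/20, after the 07/15/20 limit for the broadened windows, so for those visits the remedy lies in the analysis rules.

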4.2 Participant Exclusion

Participants found to be ineligible for A5369 by the site, study statistician(s), or data manager will be reviewed by the study chair and vice chair for confirmation of their ineligibility.

4.3 Visit Schedule and Analysis Windows

The schedule of evaluations is given in Section 6.1 the protocol. See timing of evaluations below:

- **Screening:** evaluations must be completed within 60 days prior to randomization (i.e., entry, week 0) unless otherwise specified.
- **Pre-Entry:** evaluations must be completed at least 24 hours after screening evaluations have been completed and at least 24 hours prior to entry evaluations unless otherwise specified.
- **Entry (week 0):** evaluations must occur at least 24 hours after pre-entry evaluations unless otherwise specified. Study entry or baseline is defined as the randomization date. The value used for baseline summaries will be the last evaluation on or before the randomization date. Participants must begin treatment within 72 hours after study enrollment.
- **Post-Entry:** evaluations occur after the study entry visit and vaccination #1 administration at week 0. The visit window for the post-entry evaluations is \pm 14 days.

- **Week 4** (vaccine #2 administration): weeks (2, 6]
- **Week 12** (vaccine #3 administration): weeks (10, 14]
- **Week 24** (vaccine #4 administration): weeks [22, 26]
- **Week 48**: evaluations will be completed at the participant's final on study visit and scheduled within a ± 14 days; weeks (46, 50].

Due to the delayed visits during the COVID-19 pandemic, starting 03/16/20, the visit window for week 24 and 48 was broadened from ±14 days to -14 days to +60 days. The broadened visit window was applicable to visits scheduled to occur before 04/30/20. Upon further review, the visit window was then broadened from ±14 days to -14 days to +180 days for visits that were planned to occur before 07/15/20. While +180 days was allowed, sites were still encouraged to schedule the applicable visits within +90 days. Thus, the new visit window for week 24 is weeks [22, 50] and week 48 is weeks [46, 74]

According to CM # 2, the week 24 and week 26 visits should remain separate and coordinated to be as close to 2 weeks apart as feasible, but can be up to 60 days apart. Thus, if the week 26 visit has to be delayed, it is better to postpone the week 24 visit until the week 26 visit can occur 2 weeks later, or as close to that interval as possible.

- Any deferred study vaccinations #2, #3, and #4 should be performed within 14 days from the time of the previously scheduled week 4, week 12, and week 24 visits, respectively.
- **Discontinuation Evaluations:**
 - Participants who are enrolled, but who do not receive vaccination #1 will be taken off study. No further evaluations are required. These participants will be replaced.
 - Premature Treatment Discontinuation Evaluations: Participants who prematurely discontinue study treatment prior to receiving vaccination #2 or #3 should remain on study (off study treatment) until the final visit. No further vaccinations should be administered. The participants should complete the premature treatment/study discontinuation valuation as specified in the SOE. Participants should complete the safety evaluations per protocol until study completion (clinical assessments, hematology, chemistries and VRC review).
 - Premature Study Discontinuation Evaluation: Participants who discontinue the study prior to the final visit should complete the premature treatment/study discontinuation evaluations as specified in the SOE.

The analysis windows will be formed around each study visit using the midpoints between adjacent weeks as cutoffs. If there are multiple evaluations within the window for a given visit, then the evaluation closest to the scheduled study week will be used, and the earlier measurement will be used if there are two measurements which are equally distant from the scheduled week.

5 Statistical Methods

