This Primary Statistical Analysis Plan (SAP) describes the primary and secondary outcome measures and general analytic approaches of ACTG A5369 that will be included in the primary manuscript or submitted to ClinicalTrials.gov. It has been developed to facilitate discussion of the statistical analysis components amongst the study team; and to provide agreement between the study team and statisticians regarding the statistical analyses to be performed and presented in the Primary Statistical Analysis Report (SAR). Detailed outlines of tables, figures, and coding descriptions that will be included in the Primary SAR are included in the Analysis Implementation Plan (AIP). A separate SAP for Other Objectives will be developed when results for the Primary and Secondary Objectives are known, and analyses will be presented in a separate report. Data for the Primary SAR will be downloaded once the last participant has completed 48 weeks of follow-up, all queries have been resolved, and the database frozen for analysis. The Primary SAR will be used for submission of results to ClinicalTrials.gov. Results for primary outcomes are required to be submitted within one year of the primary completion date (PCD), which is the date that the final participant is examined for the purposes of final collection of data for all of the primary outcomes. The primary immunogenicity outcome is measured at 26 weeks of participant follow-up, and the primary safety outcome data collection is completed at 48 weeks of follow-up. Thus, the PCD of this study is based on 48 weeks of follow-up. Results for secondary outcome measures for this study are due at the same time.

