2.1 Study Design

A5369 is a phase I/IIa, randomized, double-blind, placebo-controlled study that will evaluate the safety, immunogenicity, and preliminary assessment of efficacy of a novel vaccine encoding “conserved elements” (CE) of the HIV-1 Gag core protein, p24Gag, as a therapeutic vaccine in HIV-1 infected persons on antiretroviral therapy (ART) with the aim to induce potent virus-specific cytotoxic T lymphocytes (CTL) responses. The primary efficacy outcome will be based on HIV-specific immunologic assays at baseline and week 26.

Duration

Participants will be on study for a total of 48 weeks.

Sample Size The target sample size of 40 (20 p24CE; 10 full length Gag; 10 placebo) for the randomized arms is selected to detect a 0.54 difference in the probability that a participant has increased CE responses (0.64 for p24CE vaccine and 0.10 for placebo) between arms based on a two-sided Fisher's exact test with 80% power, 5% alpha level, and 10% inflation of the estimated sample size for loss-to-follow-up or unusable laboratory specimens. The study also has approximately 80% power to detect a difference of 0.85 versus 0.30 when comparing the p24CE and full-length Gag vaccine arms.

Population

HIV-infected individuals receiving ART with plasma HIV-1 RNA <50 copies/mL for at least 2 years (one “blip” allowed), current CD4 T cell counts >500 cells/mm³, and nadir CD4 T cell counts >350 cells/mm³ (by documentation or candidate recall).

Randomization and Stratification

Participants will be randomized 2:1:1 to the p24CE/full-length Gag DNA vaccine arm versus full-length Gag DNA vaccine arm versus placebo arm using the permuted block method.

Randomization will be stratified by indication of willingness to have the leukapheresis procedure at study screening. The active vaccines/placebo will be administered by intramuscular injection/electroporation.

Regimen

Arm 1: p24CE/full-length Gag DNA Vaccine Arm

p24CE1/2 pDNA 4 mg administered by injection/electroporation at week 0 and week 4. Then p24CE1/2 pDNA 2 mg admixed with full-length p55gag pDNA 2 mg administered by one injection/electroporation at week 12 and week 24.

Arm 2: Full-length Gag DNA Vaccine Arm

Full-length p55gag pDNA 4 mg administered by one injection/electroporation at week 0, week 4, week 12 and week 24

Arm 3: Placebo Arm

Placebo (Sodium Chloride for Injection, USP 0.9%) 1 ml administered by one injection/electroporation at week 0, week 4, week 12 and week 24.

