Analysis will be performed in a superiority framework, comparing between arms the change in the number of CEs with a CD4 and/or CD8 T cell response from baseline to week 26.

Major change of the study follow-up

Due to the feasibility challenges posed by the COVID-19 situation, Clarification Memo #2 was issued to broaden the visit window from ± 14 days to -14 days to +60 days, starting from 03/16/20. On April 8 2020, after further review, Letter of Amendment #3 was then issued to further broaden the visit window from +60 days to +180 days but sites were still encouraged to schedule the applicable visits within +90 days.

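### The midpoint window rule in SAP 4.3 makes no exception for week 26, so a primary specimen drawn at a permitted visit could be labelled week 24 or, under narrower conditions, week 48

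*SAP*

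**What the plan says.** SAP 2.1 fixes the time point: "The primary efficacy outcome will be based on HIV-specific immunologic assays at baseline and week 26". SAP 5.1 analyses the change from baseline to week 26 per protocol, on complete cases.

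SAP 4.3 contains several statements on timing:

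- **General visit window.** Post-entry visits have ±14 days. Protocol 6.2.3 says the same.
- **Listed ranges.** Ranges are given for weeks 4, 12, 24 and 48. The week 24 line reads "vaccine #4 administration): weeks [22, 26" (closed at both ends). Week 26 has no line.
- **COVID-19 extension.** The SAP says that "the visit window for week 24 and 48 was broadened from" ±14 days to -14/+60 days, then to -14/+180 days for visits planned before 07/15/20, with +90 days encouraged. It concludes that week 24 now runs over weeks 22 to 50 and week 48 over weeks 46 to 74. SAP 2.1 describes the later change without naming visits: it was "issued to further broaden the visit window from +60 days to +180 days". Protocol 6.2.3 broadens post-entry visits generally.
- **Gap between weeks 24 and 26.** The two visits should be "as close to 2 weeks apart as feasible, but can be up to 60 days apart".
- **Deferred vaccination.** A deferred vaccination #4 is to be given within 14 days of the originally scheduled week 24 visit. Protocol 6.2.3, Note A, has the same limit.
- **Assignment to analysis visits.** "The analysis windows will be formed around each study visit using the midpoints between adjacent weeks as cutoffs". Where several evaluations fall in one window, the one nearest the scheduled week is used. No exception is stated.

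**The concern.** A visit window tells the site when a visit may take place. An analysis window decides which visit label a value carries in the analysis. If the second is narrower than the first, a specimen collected in full compliance can lose its label.

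At week 26 the label decides whether the participant has a primary outcome. Under the complete-case rule in SAP 5.1, a week 26 specimen labelled week 24 or week 48 leaves no week 26 value, and the participant drops out of the comparison because of a labelling rule. The sensitivity analyses in 5.1 would not bring the value back. The modified ITT and stratified analyses would use the same labels, and the COVID-19 analysis concerns only delayed vaccinations #2 and/or #3. The evaluability and protocol deviation sections listed in SAP 6 might count such participants but would not restore them.

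**Working it through.** **Inputs.** Named visits at weeks 24, 26 and 48 (SAP 4.3), that is, days 168, 182 and 336. Visit windows of ±14 days, or -14/+180 days (Protocol 6.2.3; SAP 4.3). Gap between weeks 24 and 26 of about 14 and at most 60 days. Deferral limit of 14 days for vaccination #4.

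**1. The plan's own figures.** Week 24: 24 - 2 = 22 and 24 + 180/7 = 49.7. Week 48: 48 - 2 = 46 and 48 + 180/7 = 73.7. These round to the stated [22, 50] and [46, 74].

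**2. Week 26 analysis window by midpoints.**
- Lower cut-off: (24 + 26)/2 = week 25 = day 175, which is 175 - 182 = -7 days.
- Upper cut-off: (26 + 48)/2 = week 37 = day 259, which is 259 - 182 = +77 days.
- The rule does not settle a value exactly on a cut-off.

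**3. Permitted week 26 visit.** ±14 days gives weeks 24 to 28. If +180 days applies, the upper end is 26 + 180/7 = week 51.7.

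**4. Early part.** Offsets -14 to -8 (days 168 to 174) are permitted but fall below day 175, so they go to week 24. The listed week 24 range, weeks 22 to 26, also overlaps these days. At a 14-day gap, this needs a week 24 visit on days 154 to 160, which is 8 to 14 days early. Otherwise the gap must be shorter than 14 days: with week 24 on time, at most 174 - 168 = 6 days. No COVID-19 provision is involved.

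**5. Late part.** Offsets of +78 and above (day 260 on) go to week 48. Of these, +78 to +90 lie within the encouraged limit.
- At a 14-day gap, the week 24 visit must be on day 246 or later: 246 - 168 = 78 days late.
- At the 60-day maximum gap, it must be on day 200 or later: 200 - 168 = 32 days late.
- Under the 14-day deferral limit, the latest week 26 visit is 168 + 14 + 60 = day 242 (+60 days), short of day 259. On the named visits the late part then cannot occur.
- Under the SAP's broadened week 24 limit, the latest week 24 visit is day 168 + 180 = 348. Adding 14 to 60 days gives days 362 to 408 (weeks 51.7 to 58.3), well past week 37.

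**6. Visits not shown.** The schedule of evaluations is not in the available text. A visit at week W between 26 and 48 would move the upper cut-off to (26 + W)/2. As an assumption, W = 32 gives +21 days and W = 44 gives +63 days. At W = 43 the cut-off is day 241.5, below day 242, so with W of 43 or less a late specimen could leave the week 26 window even under the 14-day deferral limit.

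**7. Day counts.** Of the 195 offsets from -14 to +180, 7 go to week 24 and 103 to week 48. These are counts of days, not expected shares of participants.

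**8. What lost participants would cost (illustration only).** The planning calculation uses Fisher's exact test at 0.64 v 0.10, with "10% inflation of the estimated sample size for loss-to-follow-up or unusable laboratory specimens". The primary test is Wilcoxon, so the figures below only indicate scale.

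| Evaluable, p24CE v placebo | Exact two-sided Fisher power |
|---|---|
| 20 v 10 | 79.6% |
| 18 v 9 | 79.8% |
| 17 v 9 | 74.0% |
| 18 v 8 | 73.5% |
| 16 v 9 | 77.8% |
| 16 v 8 | 68.8% |

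The 18 v 9 row (10% off each arm) reproduces the stated 80%. Losses within the allowance cost nothing, and one more costs about 6 points. Power is not monotone in sample size, as 16 v 9 shows. Labelling losses would share the same 10% with real dropout and unusable specimens.

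**The case against.** The strongest reply is that nobody would apply the rule this way to the primary specimen. SAP 5.1 refers to each participant's week 26 visit as an identifiable event, 4.3 keeps the week 24 and week 26 visits distinct, and 3.1.1 says a laboratory supplies the response counts. The SAP's introduction adds that "coding descriptions that will be included in the Primary SAR are included in the Analysis Implementation Plan", so a nominal-visit rule may sit there. Windows might also be formed only among visits at which the assay is drawn. If those are baseline and week 26 alone, both parts disappear. If week 48 is included, the late part remains.

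This lowers the likelihood of harm but does not remove the point. The rule in 4.3 speaks of every study visit, and nothing in the SAP text exempts the primary assay or says that labels are nominal.

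A reader might infer two stronger things that the documents do not support:

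- **That nothing in 4.3 would place an early specimen at week 26.** The general ±14-day post-entry window covers days 168 to 174 for a week 26 visit. It is worded as a visit window, and the status of the listed ranges is itself unclear, so the text conflicts rather than uniformly excluding the specimen.
- **That the SAP plainly gives week 26 a +180-day window.** The protocol broadens post-entry visits generally, but SAP 4.3 names only weeks 24 and 48. The late part rests on the protocol's wording, or on what the SAP's week 50 limit for week 24 implies for the visit after it. On the named visits it fails if the 14-day limit on deferred vaccination #4 governs.

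It is also fair that the early part is an edge case.

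**Conclusion.** The point holds in a limited form, with minor to moderate severity. Followed literally, SAP 4.3 gives week 26 an analysis window of -7 to +77 days on the named visits, narrower than the permitted visit window, and the complete-case rule would then drop a participant whose specimen was relabelled.

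The early part (8 to 14 days early) arises under the ordinary window but needs an early week 24 visit or a short gap. The late part (78 or more days late) needs a visit planned before 07/15/20 and the +180-day window to govern. The passages on +180 days, on which visits were broadened, and on the 14-day deferral limit must be reconciled before it can be called possible or impossible.

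The conclusion assumes that no unseen visit changes the neighbours of week 26 and that the Analysis Implementation Plan does not override the rule. The documents do not show that anyone was affected, and the number may be zero. A reader should therefore not infer that the trial lost power.

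**What to change.** **SAP 4.3.** State that for the immunogenicity outcomes the week 26 value is the specimen from the nominal week 26 visit, that the midpoint rule does not reassign it, and that a specimen from the week 24 visit, if one is drawn, is never used as week 26. Say whether the listed ranges are visit windows or analysis windows. If the Analysis Implementation Plan already assigns by nominal visit, bring that sentence into the SAP.

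**SAP 5.1.** The broadened windows in 4.3 concern weeks 24 and 48, whereas the COVID-19 sensitivity analysis excludes only delayed vaccinations #2 and/or #3. Extend it to participants with a delayed vaccination #4 or a delayed week 26 visit.

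**Both documents.** Reconcile the +180-day window with the 14-day limit on deferred vaccination #4, and the protocol's general broadening with the SAP's naming of weeks 24 and 48 only.

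**Cost.** A few sentences and a small programming change, assuming nominal visit labels are recorded, which the available text does not show. The downside is that specimen timing becomes more variable, which the extended sensitivity analysis addresses.
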